11.6.1 Liver function tests and evaluation of PDILI

The PDILI IMP discontinuation criteria for this study are provided in [Section 6.3.1](#) with the accompanying required follow-up investigation and monitoring detailed below. All PDILI events must be reported as an AE and reported to the study site and sponsor within 24 hours of learning of their occurrence. Any PDILI event that meets the criterion for potential Hy’s Law must be reported as an AE of special interest (see [Section 11.3](#)), and, if applicable, also reported as an SAE (see [Section 11.2](#)).

Evaluation of PDILI consists of the diagnostic testing and continued monitoring included in [Table 11–3](#) (specific tests dependent on laboratory results and corresponding symptoms) and consultation with a local hepatologist (if applicable; discussed in [Section 11.6.1.1](#)). The local hepatologist is the expert usually consulted by the treating physician for assessment and management of potential hepatic disease. This would usually be a hepatologist, but may be a gastroenterologist. Additional investigation and monitoring may be required and adapted based on the diagnosis after the cause of the liver injury/abnormality is confirmed (details in [Section 11.6.1.4](#)).

The results of all monitoring, including laboratory testing and other testing, should be made available to the study site and sponsor.

All initial tests resulting in abnormal hepatic laboratory values need to be repeated, but appropriate medical action must not be delayed waiting for the repeat result.

If tests are done locally for more rapid results, a concurrent sample should also be sent to the central laboratory whenever possible. Medical care decisions are to be made initially using the most rapidly available results and a conservative approach must be taken if the results from the 2 laboratory tests are significantly different. Data from the local and central laboratory are to be recorded on the applicable eCRF pages.

When IMP is discontinued, all concomitant medications and herbal supplements that are not medically necessary should also be discontinued. In these cases, the investigator should also consider dose reduction for medically necessary concomitant medication and consider changing any medically required concomitant medication known to be hepatotoxic to a suitable alternative.

When IMP is stopped due to PDILI (as described in Section 6.3.1), IMP must be permanently discontinued unless a subsequent alternative diagnosis fully explains the hepatic findings.

Rechallenge with a substance potentially causing drug-induced liver injury is dangerous, may be fatal, and must not occur.

The table below summarizes the approach to investigate PDILI.

Table 11-3: Required investigations and follow up of PDILI

Laboratory value		Symptoms of hepatitis or hypersensitivity ^a		Immediate		Follow up	
ALT or AST	Total bilirubin ^b	NA	NA	Consultation requirements	Actions	Testing	Evaluation
≥3xULN	≥2xULN	NA	NA	Hepatology consult. ^c Medical Monitor must be notified within 24 hours (eg, by laboratory alert) and subject discussed with Medical Monitor ASAP.	Immediate, permanent IMP discontinuation. Immediate, temporary or permanent, IMP discontinuation.	Essential: Must have repeat liver chemistry values and additional testing completed ASAP (see Section 11.6.1.3); recommended to occur at the site with HCP.	Monitoring of liver chemistry values at least twice per week until values normalize, stabilize, or return to within Baseline values.
≥5xULN	NA	NA	NA				
≥3xULN	NA	Yes	Yes				
≥3xULN (and ≥2x Baseline) and <5xULN	<2xULN	No	No	Discussion with Medical Monitor required if the criterion that allows for IMP continuation is met.	Further investigation – immediate IMP discontinuation not required (see Section 11.6.1.2).	Not required unless otherwise medically indicated (at discretion of investigator).	

Table 11-3: Required investigations and follow up of PDILI

Laboratory value		Immediate		Follow up		
ALT or AST	Total bilirubin	Symptoms of hepatitis or hypersensitivity ^a	Consultation requirements	Actions	Testing	Evaluation
≥5xULN (and ≥2x Baseline)	<2xULN	No	Discussion with Medical Monitor required.	Immediate, permanent IMP discontinuation.	Essential: Every attempt must be made to have repeat liver chemistry values and additional testing completed within 48 hours at the site with HCP (see Section 11.6.1.3)	Monitoring of liver chemistry values at least twice per week until values normalize, stabilize, or return to within Baseline values. ^d

ALP=alkaline phosphatase; ALT=alanine aminotransferase; ASAP=as soon as possible; AST=aspartate aminotransferase; HCP=healthcare practitioner; IMP=investigational medicinal product; NA=not applicable; PDILI=potential drug-induced liver injury; ULN=upper limit of normal

^a Hepatitis symptoms include fatigue, nausea, vomiting, and right upper quadrant pain or tenderness; hypersensitivity symptoms include eosinophilia (>5%), rash, and fever (without clear alternative cause).

^b If the subject also has ≥2xULN ALP, the possibility of an indication of biliary obstruction should be discussed with the Medical Monitor.

^c Details provided in Section 11.6.1.1. The local hepatologist is the expert usually consulted by the treating physician for assessment and management of potential hepatic disease. This would usually be a hepatologist, but may be a gastroenterologist.

^d Unless an alternative monitoring schedule is agreed by the investigator and UCB responsible physician. Determination of stabilization is at the discretion of the investigator in consultation with the hepatologist (as applicable) and UCB responsible physician, as needed.

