11.6.1.2 Immediate action: determination of IMP discontinuation

All PDILI events require immediate action, testing, and monitoring.

The immediate action is dependent on the laboratory values and symptoms of hepatitis or hypersensitivity and ranges from continuation of IMP (followed by immediate investigation) to immediate and permanent discontinuation (see Section 6.3.1 and Table 11-3 for details).

When IMP is discontinued, all concomitant medications and herbal supplements that are not medically necessary should also be discontinued. The investigator should also consider dose reduction for medically necessary concomitant medication and consider changing any medically required concomitant medication known to be hepatotoxic to a suitable alternative.

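### Table 11-3 puts the same child with ALT or AST at 5xULN or more under two rows that differ on the hepatology consult, and its row for continuing drug waives testing that the section text requires.

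*Protocol*

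**What the plan says.** Rows are counted from the top of Protocol Table 11-3, across both its pages.

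- **Second row.** The trigger is "≥5xULN NA NA NA": ALT or AST at or above 5xULN, with bilirubin and symptoms not considered. It stands in the block formed by the first three rows. The consultation cell of that block asks for a hepatology consult and adds "Medical Monitor must be notified within 24 hours (eg, by laboratory alert) and subject discussed with Medical Monitor ASAP". The testing cell reads "Must have repeat liver chemistry values and additional testing completed ASAP (see Section 11.6.1.3); recommended to occur at the site with HCP".
- **Last (fifth) row.** The trigger is "≥5xULN (and ≥2x Baseline"), bilirubin below 2xULN and no symptoms of hepatitis or hypersensitivity. Consultation is a discussion with the Medical Monitor. Testing reads "Every attempt must be made to have repeat liver chemistry values and additional testing completed within 48 hours at the site with HCP".
- **Fourth row (drug may continue).** The trigger is ALT or AST at least 3xULN, at least 2x Baseline and below 5xULN, with bilirubin below 2xULN and no symptoms. The action is further investigation without immediate discontinuation. The testing cell reads "Not required unless otherwise medically indicated (at discretion of investigator").

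Section 11.6.1.2 says "All PDILI events require immediate action, testing, and monitoring". Section 11.6.1 says every initial abnormal hepatic value has to be repeated. Section 11.6.1.1 requires notice to the Medical Monitor within 24 hours for PDILI events in general, and involves the local hepatologist where that is required. Section 6.3.1 lists the fourth-row state as one of its PDILI criteria.

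**The concern.** A site with one laboratory result should find one row. Here a symptom-free child at 5xULN or more with bilirubin below 2xULN finds two, and no rule says which prevails. One leads to a hepatology consult; the other does not mention it. A site whose patient meets the fourth row reads in the table that testing is discretionary, and in the text beneath it that testing is required.

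The children are between 1 month and 4 years old, and Section 11.6.1 presents this work-up as required follow-up. If sites resolve the conflict differently, children with the same result get different work-ups, and the information available for judging whether lacosamide was the cause varies by site.

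**Working it through.** The plan states no figure to reproduce. The check is whether the row conditions overlap, and then what each overlapping row demands.

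**Step 1. Does the Baseline condition separate the second and last rows?**

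Inputs: exclusion criterion 22 (Section 6.2) excludes ALT or AST above 2xULN. A result up to 25% above that limit, 2 × 1.25 = 2.5xULN, may be retested once.

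The smallest fold-rise at the 5xULN trigger is 5 divided by Baseline in xULN:

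| Baseline ALT/AST | Fold-rise at 5xULN | At least 2x Baseline? |
|---|---|---|
| 2xULN (entry limit) | 5/2 = 2.5 | Yes |
| 2.5xULN (retest ceiling) | 5/2.5 = 2.0 | Yes |
| 3xULN (above both) | 5/3 = 1.67 | No |

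For a child who meets criterion 22 the condition is always satisfied. Given bilirubin below 2xULN and no symptoms, such a child meets both rows. A grid of 4 enzyme levels (5, 6, 8, 12xULN), 3 bilirubin levels (0.5, 1, 1.9xULN) and 5 Baselines (0.5 to 2.5xULN) gives 4 × 3 × 5 = 60 combinations; all 60 meet both. Only a Baseline above 2.5xULN can leave the second row alone.

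**Step 2. What do the two rows demand?**

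| Requirement | Second row | Last row |
|---|---|---|
| Drug action | Immediate, permanent stop | Immediate, permanent stop |
| Hepatology consult | Yes | Not stated |
| Medical Monitor, 24-hour notice | In the row | Not in the row, but applied by 11.6.1.1 |
| Testing | Must be completed, as soon as possible | Every attempt, within 48 hours |
| Testing at the site | Recommended | Part of the requirement |
| Liver chemistry monitoring | At least twice weekly | At least twice weekly |

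The firm difference is the hepatology consult. The testing cells differ in strength of obligation, time limit and location.

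**Step 3. The fourth row against the text.**

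It overlaps no other row, so the conflict is with the text alone. Section 6.3.1 makes this state a PDILI criterion; Section 11.6.1.2 requires testing for all PDILI events; Section 11.6.1 requires abnormal values to be repeated; the table cell makes testing discretionary. Section 11.6.1.3 adds another trigger: its measurements are required when there is a reasonable possibility that the drug was the cause.

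Not every symptom-free child between 3xULN and 5xULN is affected. A bilirubin of 2xULN or more moves the child to the first row. A Baseline of 2xULN with ALT at 3xULN gives 3/2 = 1.5, short of the required 2x Baseline, so the fourth row does not apply.

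**The case against.** The case against says this is untidy wording with little consequence. Much of it is fair, and several stronger readings should be set aside.

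- A reader might infer that the last row drops the 24-hour notice to the Medical Monitor. The row is silent, but Section 11.6.1.1 applies the notice to PDILI events generally, and Section 11.6.1 requires PDILI events to be reported to the sponsor within 24 hours. There is no conflict on this.
- A reader might infer that the two rows treat the drug differently. They do not: both require immediate, permanent discontinuation, in line with Section 6.3.1.
- A reader might see opposing deadlines. Testing done as soon as possible will normally also fall within 48 hours, so the cells are largely compatible.
- A reader might conclude that a fourth-row child could go wholly untested. The repeat rule in Section 11.6.1 still applies, and the row itself calls for further investigation. The waiver may be meant only for the additional etiology tests, since Section 11.6.1 lets specific tests depend on results and symptoms. The table does not say so, and Section 11.6.1.2 makes no exception.
- A reader might fear distorted PDILI counts. SAP Section 10.3 counts PDILI from the protocol criteria at all laboratory assessments, so those counts do not depend on which work-up row a site followed.

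It can also be said that Sections 11.6.1 and 11.6.1.1 call for a hepatologist only where applicable or required, and that the last row's footnote on stabilization mentions one. That softens the difference, but neither section says when the consult is required, which sends the reader back to a table with two answers.

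**Conclusion.** The point holds in two limited parts. First, every eligible child with ALT or AST of at least 5xULN, bilirubin below 2xULN and no symptoms meets two rows, which differ on the hepatology consult and, to a lesser degree, on the testing wording. Second, for the fourth-row child, the table's testing cell conflicts literally with Sections 11.6.1 and 11.6.1.2.

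This is a contradiction in written safety procedures. It has no bearing on sample size, power or type I error. The documents give no expected frequency of such elevations, so the number of children affected cannot be stated.

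Two assumptions matter. The table was read from PDF, and the blank consultation and testing cells of the second row are taken as merged with the row above; if they were truly blank, the second row would still differ from the last. The overlap being complete also assumes that Baseline respects the entry limit; a pre-dose value above 2.5xULN could separate the rows.

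**What to change.** Reconcile Table 11-3 so that each combination of ALT/AST, bilirubin and symptoms leads to one consultation requirement and one testing requirement. Either make the second and last rows mutually exclusive or give them the same cells.

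Make the fourth row's testing cell agree with Sections 11.6.1 and 11.6.1.2, for example by stating whether the waiver covers only the additional etiology tests or also the repeat liver chemistry. Repeating the 24-hour notice in the last row is not needed to remove a conflict.

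Which consultation and testing requirement applies is for the sponsor's clinical team; this review proposes none. The cost is wording in a clarification letter or the next protocol amendment, with no change to the analysis.

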11.6.1.1 Consultation with Medical Monitor and local hepatologist

Potential drug-induced liver injury events require notification of the Medical Monitor within 24 hours (eg, by laboratory alert), and the subject must be discussed with the Medical Monitor as soon as possible. If required, the subject must also be discussed with the local hepatologist. The local hepatologist is the expert usually consulted by the treating physician for assessment and management of potential hepatic disease. This would usually be a hepatologist, but may be a gastroenterologist. If determined necessary, this discussion should be followed by a full hepatology assessment (see Section 11.6.1.3) and SAE report (if applicable).

11.6.1.2 Immediate action: determination of IMP discontinuation

All PDILI events require immediate action, testing, and monitoring.

The immediate action is dependent on the laboratory values and symptoms of hepatitis or hypersensitivity and ranges from continuation of IMP (followed by immediate investigation) to immediate and permanent discontinuation (see Section 6.3.1 and Table 11-3 for details).

When IMP is discontinued, all concomitant medications and herbal supplements that are not medically necessary should also be discontinued. The investigator should also consider dose reduction for medically necessary concomitant medication and consider changing any medically required concomitant medication known to be hepatotoxic to a suitable alternative.

11.6.1.3 Testing: identification/exclusion of alternative etiology

The measurements and additional information required for the assessment of PDILI events when there is a reasonable possibility that they may have been caused by the IMP are detailed in Table 11-4 (laboratory measurements) and Table 11-5 (additional information). Results of the laboratory measurements and information collected are to be submitted to the sponsor on the corresponding eCRF. If the medical history of the subject indicates a requirement for other assessments not included below, these additional assessments should be completed and submitted, as applicable.

All blood samples should be stored, if possible. If tests are done locally for more rapid results, a concurrent sample must also be sent to the central laboratory.

The following measurements are to be assessed:

Table 11–4: PDILI laboratory measurements

Virology-related	Hepatitis A IgM antibody
	HBsAg
	Hepatitis E IgM antibody
	HBcAb-IgM
	Hepatitis C RNA
	Cytomegalovirus IgM antibody
	Epstein-Barr viral capsid antigen IgM antibody (if unavailable, obtain heterophile antibody or monospot testing)
Immunology	Anti-nuclear antibody (qualitative and quantitative)
	Anti-smooth muscle antibody (qualitative and quantitative)
	Type 1 anti-liver kidney microsomal antibodies (qualitative and quantitative)
Hematology	Hematocrit
	Hemoglobin
	Platelet count
	RBC count
	WBC count
	Differential count
Urinalysis	Toxicology screen
Chemistry	Amylase
	Bilirubin (If total bilirubin $\geq 1.5 \times \text{ULN}$, obtain fractionated bilirubin to obtain % direct bilirubin)
	Serum CPK and LDH to evaluate possible muscle injury causing transaminase elevation
	AST
	ALT
	ALP
	GGT
	Albumin
Additional	Prothrombin time/INR ^a
	PK sample

ALP=alkaline phosphatase; ALT=alanine aminotransferase; AST=aspartate aminotransferase; CPK=creatinine phosphokinase; GGT=gamma-glutamyl transferase; HBcAb-IgM=hepatitis B core antibody-IgM; HBsAg=hepatitis B surface antigen; IgM=immunoglobulin M; INR=international normalized ratio; LDH=lactate dehydrogenase; PDILI=potential drug-induced liver injury; PK=pharmacokinetic; RBC=red blood cell; RNA=ribonucleic acid; ULN=upper limit of normal; WBC=white blood cell

^a Measured only for subjects with ALT >8xULN, elevations in total bilirubin, and symptoms of hepatitis or hypersensitivity. Hepatitis symptoms include fatigue, nausea, vomiting, and right upper quadrant pain or tenderness; hypersensitivity symptoms include eosinophilia (>5%), rash, and fever (without clear alternative cause).

The following additional information is to be collected:

Table 11–5: PDILI information to be collected

New or updated information
Concomitant prescription and over-the-counter medications (eg, acetaminophen, herbal remedies, vitamins); dosages and dates should be included.
Pertinent medical history, including the following: 
 • History of liver disease (eg, autoimmune hepatitis, nonalcoholic steatohepatitis or other “fatty liver disease”) • Adverse reactions to drugs • Allergies • Relevant family history or inheritable disorders (eg, Gilbert’s syndrome, alpha-1 antitrypsin deficiency) • Recent travel • Progression of malignancy involving the liver (Note: Metastatic disease to the liver, by itself, should not be used as an explanation for significant AST and/or ALT elevations.)
The appearance or worsening of clinical symptoms of hepatitis or hypersensitivity (eg, fatigue, nausea, vomiting, right upper quadrant pain or tenderness, decreased appetite, abdominal pain, jaundice, fever, or rash)
Recent clinically significant hypotension or hypoxemia with compromised cardiopulmonary function
Results of liver imaging or liver biopsy, if done
Results of any specialist or hepatology consult, if done
Any postmortem/pathology reports

ALT=alanine aminotransferase; AST=aspartate aminotransferase; PDILI=potential drug-induced liver injury

11.6.1.4 Follow-up evaluation

Potential drug-induced liver injury events require follow-up monitoring as described in Table 11–3. Monitoring should continue until liver chemistry values normalize, stabilize, or return to Baseline. Determination of stabilization is at the discretion of the investigator in consultation with the hepatologist (as applicable) and UCB responsible physician, as needed.

11.7 Other safety measurements

11.7.1 Physical examination

Physical examinations will be performed according to the tabular schedule of study procedures (Section 5.2) by a medically qualified clinician licensed to perform the examination. Subsequent to Visit 1, clinically significant physical examination findings should be reported as AEs.

11.7.1.1 Complete physical examination

The complete physical examination will include cardiac and respiratory function via auscultation, temperature, and review of all body systems.

11.7.1.2 Brief physical examination

The brief physical examination will include review of the following body systems:

- Cardiovascular
- Pulmonary
- Abdominal (hepato-gastrointestinal)
- Dermatologic

11.7.2 Neurological examination

Neurological examinations will be performed according to the tabular schedule of study procedures (Section 5.2) by a medically qualified clinician with documented training in the conduct of neurological examinations. If possible, the same clinician should conduct all neurological examinations for the same subject during the study. The investigator or subinvestigator is responsible for confirming the diagnosis of partial-onset seizures. Subsequent to Visit 1, clinically significant neurological examination findings should be reported as AEs.

11.7.2.1 Complete neurological examination

The complete neurological examination will include selected assessment of general neurological status (level of consciousness, mental status, speech), cranial nerves, reflexes, motor system (general motor status, muscle strength, muscle tone), coordination/cerebellar function, and sensation.

11.7.2.2 Brief neurological examination

The brief neurological examination will include selected assessment of general neurological status, reflexes, muscle strength, and coordination/cerebellar function.

11.7.3 Vital signs, body weight, and height

Noninvasive BP (systolic and diastolic) and pulse rate will be measured at clinic visits after at least 3 minutes at rest in a supine position, according to the tabular schedule of study procedures (Section 5.2). Assessment of orthostatic changes will be as follows: after the 3 minute measurement in a supine position, the subject is asked to stand up, and BP and pulse rate are taken 1 minute and 3 minutes after standing up, as feasible.

Body weight will be determined without shoes and wearing light clothing, and height will be measured without shoes. Body weight and height will be assessed according to the tabular schedule of study procedures (Section 5.2).

11.7.4 12-lead ECG

Standard 12-lead ECGs will be performed according to the tabular schedule of study assessments (Section 5.2). Care should be taken to assure proper lead placement and quality ECG recordings. Two interpretable recordings will be performed prior to any blood draws and vital signs assessment and, if possible, with the subject in a supine position for 5 minutes preceding the ECG recording and the subject should be motionless during the recording. The second recording will be conducted approximately 20 to 30 minutes after the first recording.

11.7.5 Overall ECG interpretation

Electrocardiograms will be reviewed locally by the investigator, subinvestigator, or qualified designated reader and at a central ECG laboratory. If the reading identifies second or third degree AV block, a QTc \geq 500ms, or another abnormal ECG finding that is assessed by the investigator to be clinically significant, then the ECG should be repeated on the same day. If the clinically significant abnormality is confirmed by the repeat ECG, then the subject must be withdrawn from the study (see Section 6.3). The investigator may consult with the cardiologist at the central ECG laboratory to confirm the presence of a clinically significant ECG abnormality. It remains the responsibility of the investigator to decide whether an ECG finding is of clinical significance on the basis of the complete clinical picture and whether this finding influences the subject's participation in the study.

